# 8. SAFETY ASSESSMENTS

## 8.1. Extent of Exposure

The following exposure and compliance parameters will be summarized descriptively by treatment:

- Total number of days exposed, defined as date of last dose of study drug date of first dose of study drug + 1.
- Number of doses administered, calculated from the in-clinic dose at Baseline and the subject dose diary. If a subject is exposed to study drug for more than 1 day, and returns no diary records, then the total number of doses is regarded to be missing. Otherwise, for any day for which there is no diary record, it is assumed that no study drug was administered at home.
- Percent compliance will be calculated as the (Number of Doses Administered) / (Number of Days Exposed) \* 100. Number of missed doses will be based on data from the summary of missed doses form.
- Subject compliance, defined as ≥80% compliance while enrolled in the study. If the percentage of study medication compliance cannot be computed, the subject is assumed to be less than 80% compliant.

A subject will be compliant with the dosing regimen if they applied  $\geq 80\%$  of the expected doses. Expected number of doses is based on length of time enrolled in the treatment-phase of the study.

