6.5 Study Intervention Compliance

At Visit 2, study product will be dispensed, and participants will be instructed on how to apply cream and will apply the study product application under supervision. During the study, participants will self-administer study product(s) at home and will record the time of study product application in a daily diary provided by the study site. Participants will be instructed to maintain the same approximate dosing time chosen at the beginning of the study for their full study participation. Compliance with study product will be assessed at each visit based on diary entries. Participants will be instructed to bring all used and unused tubes with them to each study visit. If a tube has been lost, discarded, or forgotten by the participant, then the site personnel will make a notation of this on the drug accountability logs. Forgotten tubes should be returned by the participant at the next study visit. Unopened tubes and opened, partially used tubes or tubes with foil overlay removed may only be re-dispensed once to study participants. A new tube may be dispensed if the current tube does not contain sufficient study product to last until the next visit. All tubes, including empty tubes, will be collected at Visit 8. Deviation(s) from the prescribed dosage regimen should be recorded.

A record of the quantity of study product dispensed to and administered by each participant must be maintained and reconciled with study product and compliance records. Intervention start and stop dates, including dates for intervention delays, will also be recorded.

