8.1.4 Instructions for Dosing Regimen

Participants will self-administer study product at home, QD, and will record the time of application in a daily diary provided by the study site.

Application Instructions

Participants will be instructed to:

- Treat all lesions in intertriginous areas, both newly appearing lesions and lesions that have improved or cleared during the study
 - Note: Participants may treat plaque PSO in other areas according to instructions provided in the USPI. No other treatment for scalp PSO is permitted during the study.
- Apply cream to dry, clean skin in an amount sufficient to completely cover each lesion with a thin layer
- Continue to lightly rub any residual cream visible on the disease-affected skin until it is no longer visible
- Wash hands after application, unless treating lesions on the hands or fingernails

Timing of Application

Participants will be instructed to:

- Maintain the approximate time of day for dosing at home throughout their full study participation
- Record the time of application in the daily diary
- Apply cream at least 30 minutes prior to bedtime if their chosen application time is in the evening
- Avoid swimming, bathing, showering, or strenuous activities for at least 2 hours after application

Missed Doses

A missed daily dose will be recorded as a protocol deviation.

Participants will be instructed that if a dose is missed, they should continue dosing the next day and should not apply more than QD to make up for the missed dose on the previous day.

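### Percent compliance counts doses, not days with a dose, so recorded extra applications can offset missed days and a participant can be classed compliant with fewer than 80% of days treated

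*SAP*

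**What the plan says.** All the compliance rules are in SAP 8.1.

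- **Percentage:** "Percent compliance will be calculated as the (Number of Doses Administered) / (Number of Days Exposed"), multiplied by 100.
- **Numerator:** "Number of doses administered, calculated from the in-clinic dose at Baseline and the subject dose diary". If diary records exist, "for any day for which there is no diary record, it is assumed that no study drug was administered at home". There is no matching rule for a day with more than one record.
- **Denominator:** "Total number of days exposed, defined as date of last dose of study drug" minus the date of the first dose, plus 1.
- **Class:** "Subject compliance, defined as ≥80% compliance while enrolled in the study". No upper limit is given.
- **Second wording of the class:** at least 80% of expected doses must have been applied. "Expected number of doses is based on length of time enrolled in the treatment-phase of the study". This wording has no upper limit or daily maximum either.
- **Missed doses:** these are counted from a separate form and do not enter the percentage.

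On the protocol side, the regimen is once daily (Sections 4.3 and 6.1). Under Section 8.1.4, participants who miss a dose continue the next day and "should not apply more than QD to make up for the missed dose on the previous day". The same section makes each missed daily dose a protocol deviation. Section 6.5 bases compliance on diary entries and adds: "Deviation(s) from the prescribed dosage regimen should be recorded".

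**The concern.** For a once-daily regimen, the natural measure of adherence is the share of days on which the product was applied. The SAP measures something else: the total number of applications divided by the number of days. The two agree only when no day carries more than one counted dose.

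Where a day does carry more than one, under-use and over-use offset each other within a participant. A missed day followed by a doubled day scores 2/2 = 100%, although Protocol 8.1.4 tells participants not to do this. Day 1 offers another route. The in-clinic dose is added to the diary doses, so a participant who also has a diary entry for that day is credited with two doses.

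What is at stake is how the compliance summary can be read. A reader will take the proportion compliant as a description of how closely about 30 participants kept to daily use. As defined, it can count irregular use as full adherence, and no listed compliance parameter counts days with more than one application.

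**Working it through.** **Inputs**

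- Treatment duration is up to 12 weeks (Protocol 4.1, SAP 3.1): 12 × 7 = 84 days. As a check I also use 85 days, the Week 12 target day in SAP 5.3.
- The cut-off is 80% (SAP 8.1).
- Assumption: extra applications are recorded in the diary, at most two per treated day in the examples below. The documents give no frequency for this.

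The plan contains no worked compliance figure to reproduce. The 80% is a fixed cut-off.

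**Formulas**

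Let D be days exposed, T days with at least one application, and E extra applications on those days.

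- SAP 8.1: 100 × (T + E)/D
- At most one dose counted per day: 100 × T/D

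**Doses needed over 84 days**

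0.80 × 84 = 67.2, so 68 doses are needed: 68/84 = 81.0%, whereas 67/84 = 79.8%. With E = 0 a compliant participant can miss at most 84 − 68 = 16 days. Because the formula needs only T + E ≥ 68, each recorded extra dose allows one more untreated day.

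| Pattern over 84 days | T | E | Untreated days | SAP formula | Days treated |
|---|---|---|---|---|---|
| No extras | 68 | 0 | 16 | 81.0% | 81.0% |
| One extra dose (e.g. Day 1) | 67 | 1 | 17 | 81.0% | 79.8% |
| Ten extras | 58 | 10 | 26 | 81.0% | 69.0% |
| Fourteen extras | 54 | 14 | 30 | 81.0% | 64.3% |
| 24 missed days, all made up | 60 | 24 | 24 | 100.0% | 71.4% |
| Alternate days, doubled | 42 | 42 | 42 | 100.0% | 50.0% |
| Every treated day doubled, lowest T that passes | 34 | 34 | 50 | 81.0% | 40.5% |

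The SAP classes every row as compliant. With at most one dose counted per day, only the first row remains compliant.

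**Check at 85 days**

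0.80 × 85 = 68, so 68 doses are again needed (68/85 = 80.0%). With no extras, 17 days can be missed. With every treated day doubled, 34 treated days suffice, leaving 51 untreated (34/85 = 40.0% of days). The pattern is the same.

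**Day 1 alone**

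One additional counted dose is worth 1/84 = 1.2 percentage points. A participant with no missed day would score 85/84 = 101.2%. For a participant with 67 treated days it moves the result across the cut-off, from 79.8% to 81.0%.

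**Effect on the summary**

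With 30 participants, one reclassified participant changes the proportion compliant by 1/30 = 3.3 percentage points.

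**The case against.** The strongest objection is that the problem may never arise. Participants record the time of application in a daily diary, and the SAP treats diary records by day. If the form holds one entry per day, the home-dose count is already a count of days. The eCRF and its completion guidelines would settle this, but they are not among the documents. This objection stands as a limit. The documents neither state nor exclude more than one entry per day, so misclassification is possible but not shown. It does not remove the Day 1 question, because the in-clinic dose is added to the diary count.

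A second objection is that the expected-doses sentence can be read as a daily cap, since once-daily use implies one expected dose per day. But that sentence fixes the number of doses expected. It does not say that an unscheduled second application is left out of the doses applied, so the reading is available but not secured.

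Third, missed days do not disappear. They are counted from the missed-dose form, each is a protocol deviation under Protocol 8.1.4, and SAP 6.2 summarises and lists deviations. SAP 5.1 reports maxima, so a value above 100% would show. This stands. A participant who misses and doubles in equal measure, however, does not exceed 100%, and the SAP gives no rule for reconciling such a percentage with the missed-dose count.

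Fourth, the larger patterns in the table need 10 to 42 recorded extra applications from participants told to apply once daily. Nothing in the documents suggests such frequencies. They show what the rule permits, not what is expected.

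A reader might also infer that the Week 12 response or the TEAE rates are in doubt. The documents do not support that. ITT is the only analysis set (Protocol 9.2, SAP 5.2), there is no per-protocol set and no inferential testing, and the visible text uses compliance in no efficacy or TEAE analysis.

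**Conclusion.** The point holds in a conditional form. As written, SAP 8.1 credits recorded extra applications against missed days, and a participant can be classed compliant with fewer than 80% of days treated. One extra counted dose lowers the required coverage from 68 to 67 of 84 days. Fourteen lower it to 54 of 84 (64%). The limit at two applications per treated day is 34 of 84 (40%).

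This rests on the diary holding more than one application on a day, or a Day 1 entry in addition to the in-clinic dose. The frequency of either is unknown and may be zero. It would go too far to say that under-treated participants will in fact be classed compliant.

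The consequence is confined to the descriptive compliance percentage and the compliant class. This is a minor improvement to a definition, worth making because the stated numerator does not match a once-daily regimen.

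**What to change.** In SAP 8.1, define the compliance numerator as the number of days with at least one recorded application, in-clinic or diary, counting at most one per day. Apply this numerator both to the percentage and to the rule on 80% of expected doses. State that an in-clinic dose and a diary entry on Day 1 together count as one treated day.

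Keep the total number of doses as an exposure figure. If the diary captures more than one application per day, report separately the number of such days and the number of participants with any.

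The cost is a few lines of SAP wording and one derivation from data already collected. The downside is that some compliance percentages may be slightly lower. If the diary allows only one entry per day, the percentages stay as they are, apart from any Day 1 double count.

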# 8.2. Adverse Events

All AE summaries will be restricted to TEAEs, which are defined as those AEs that occurred after dosing and those pre-existing AEs (prior to first application of study treatment) that worsened during the study. If it cannot be determined whether the AE is treatment emergent due to a partial onset date, then it will be counted as TEAE. Verbatim terms in the eCRFs will be mapped to SOCs and PTs using MedDRA (Version 26.0).

#### Imputation of start and end dates of AEs

To calculate duration of AEs, the following rules will be used where applicable to impute partial or completely missing start dates or end dates:

- If only the day is missing for a start date, the 1st of the month will be imputed. If the new estimated date falls before the date of first dose, while the known month and year match the month and year of the first dose, the date of first dose will be used as the new estimated date. The AE will be considered as a treatment-emergent AE (TEAE).
- If only the day is missing for an end date, the last day of the month will be imputed. If the new estimated date falls after the date of last study visit, the date of last study visit will be used as the new estimated date. Last study visit is defined as the Week 13 visit.

- If both the day and the month are missing for a start date or end date, no imputation will be used, and the duration will not be calculated. However, if the year of start is the same or greater than the year of the first dose date, the AE will be considered as a TEAE.
- If the start date or end date is completely missing, duration will not be calculated. However, an event with completely missing start date will be considered as a TEAE.

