8.4.1 Time Period and Frequency for Collecting AE and SAE Information

All AEs and SAEs will be collected from the signing of the ICF until the final visit at the time points specified in the SoA (Section 1.3).

All SAEs will be recorded in the EDC and reported on the required form to the Sponsor or designee immediately and under no circumstance should this exceed 24 hours, as indicated in Appendix 3. The Investigator will submit any updated SAE data to the Sponsor or designee within 24 hours of it being available.

Investigators are not obligated to actively seek information on AEs or SAEs after conclusion of the study participation. However, if the Investigator learns of any SAE, including a death, at any time after a participant has been discharged from the study, and the Investigator considers the event to be reasonably related to the study product or study participation, the Investigator must promptly notify the Sponsor.

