# 3. STUDY DESIGN

### 3.1. Overall Design

This is a single-group, open-label, multicenter study to evaluate the safety and efficacy of VTAMA (tapinarof) cream, 1% in the treatment of plaque PSO in intertriginous areas. Participants will treat plaque PSO in intertriginous areas with VTAMA (tapinarof) cream, 1% QD for 12 weeks. Efficacy of the treatment of plaque PSO in intertriginous areas will be assessed with a PGA evaluation only of intertriginous areas (iPGA).

Study duration:

- The study duration will be up to 17 weeks.
- The treatment duration will be up to 12 weeks.
- The follow-up period will be up to 1 week.

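### The partial-date rules in SAP 8.2 never look at the end date, so an adverse event known to have ended before the first dose can be counted as treatment-emergent

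*SAP*

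**What the plan says.** The opening of SAP 8.2 defines TEAEs as "those AEs that occurred after dosing and those pre-existing AEs (prior to first application of study treatment) that worsened during the study". It restricts all AE summaries to TEAEs and adds a default for incomplete onset dates: "If it cannot be determined whether the AE is treatment emergent due to a partial onset date, then it will be counted as TEAE".

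The subsection on imputing AE start and end dates then gives three rules that settle TEAE status.

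- **Start day missing.** The first of the month is imputed. If that precedes the first dose but the month and year are those of the first dose, "the date of first dose will be used as the new estimated date", and the event is a TEAE.
- **Start day and month missing.** Nothing is imputed and no duration is calculated. The event is a TEAE if its start year equals or follows the first-dose year.
- **Start wholly missing.** No duration is calculated, but "an event with completely missing start date will be considered as a TEAE".

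None of these mentions the end date. An end date lacking only its day is set to the last day of the month, capped at the last study visit.

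Protocol 8.4.1 sets the collection period: "All AEs and SAEs will be collected from the signing of the ICF until the final visit". Pre-dose events will therefore be in the database.

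**The concern.** An AE that ended before the first application did not occur after dosing and cannot have worsened on treatment. Its recorded end date settles its status, even when its start date is incomplete. The default at the top of SAP 8.2 is limited to events whose status is unknowable, whereas the imputation rules carry no such limit. The two parts of the section can therefore classify the same record differently.

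Two things are at stake. Pre-treatment events can enter the TEAE tables, which are the only AE summaries planned. In the day-missing rule the derived start can also fall after the recorded end, so the duration in the AE listing is impossible.

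The SAP already applies the missing logic elsewhere: Section 6.6 separates prior from concomitant medication by stop date, including partial stop dates. The AE rules have no equivalent.

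**Working it through.** The documents state no figure on this point, so there is nothing to reproduce. The check applies the three rules literally to dated examples.

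**Inputs**

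- Pre-dose period. From SAP 3.1: "The study duration will be up to 17 weeks", of which at most 12 weeks are treatment and at most 1 week is follow-up. The remainder is 17 - 12 - 1 = 4 weeks at most. This is inferred from the three durations.
- Planned size: about 30 participants (SAP 4).
- Duration: SAP 8.2 lists it in days but gives no formula. Both E - S and E - S + 1 are shown, where E is the end date and S the start date used. This is an assumption.

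**Worked cases, first dose on 20 March 2023 (illustrative)**

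| Start recorded | End recorded | Start used | TEAE by rule | E - S | E - S + 1 |
|---|---|---|---|---|---|
| March, day unknown | 5 March | 20 March | yes | 5 - 20 = -15 | -14 |
| March, day unknown | 10 March | 20 March | yes | -10 | -9 |
| March, day unknown | 19 March | 20 March | yes | -1 | 0 |
| March, day unknown | March, day unknown (set to 31 March) | 20 March | yes | 11 | 12 |
| Year only (2023) | 10 March | none | yes | not calculated | not calculated |
| Wholly missing | 10 March | none | yes | not calculated | not calculated |
| February, day unknown | 10 March | 1 February | no | 37 | 38 |

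Rows 1 to 3, 5 and 6 are wrong: each event ended before dosing yet is a TEAE. Row 4 is truly ambiguous, so the default to TEAE is reasonable. Row 7 is classified correctly.

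**Is the day-missing result general?** Take every first-dose date in a 365-day year and every earlier end date in the same month. A month of n days gives n(n - 1)/2 combinations:

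7 x 465 + 4 x 435 + 378 = 3255 + 1740 + 378 = 5373.

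- All 5373 are flagged as TEAEs.
- Under E - S, all 5373 durations are negative.
- Under E - S + 1, the duration is zero when the event ended the day before dosing. That is 365 - 12 = 353 combinations. The other 5373 - 353 = 5020 (93.4%) are negative, down to 1 - 31 + 1 = -29 days.

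These are date combinations, not expected events.

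**Calendar reach.** Assume a full 28-day pre-dose period with onsets spread evenly over it and first doses spread evenly over the year. About 52% of pre-dose onset days then fall in the first-dose month and about 96% in the first-dose year. The rules would therefore apply to many pre-dose onsets if the relevant part of the date were missing.

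**Weight of one participant.** 1/30 = 3.3 percentage points. SAP 8.2 counts a participant once at each level of summary, so this is a maximum. It applies only if the participant has no other TEAE at that level.

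**With an end-date condition.** All 5373 combinations become non-TEAE. Keeping the first-of-month start, the row 1 duration becomes 5 - 1 = 4 days, or 5 with the added day. No duration is negative, and under E - S + 1 the smallest is 1 day.

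**The case against.** The best defence is that the opening of SAP 8.2 governs. It defaults to TEAE only when status is unknowable, and the imputation rules are introduced as a means of calculating duration. Read together, an event known to have ended before dosing would not be a TEAE, and a careful programmer might code it so. This has some force, but the imputation rules assign TEAE status themselves without repeating the limit. Even on this reading, the imputed start would still fall after the recorded end.

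The consequence is also small, and this stands. The study is single-arm and descriptive with no inferential testing, and the error overstates harm. All AEs are listed with onset date, end date and duration, so an impossible duration could be noticed on review.

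Several stronger readings are tempting, but the documents do not support them:

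- A reader might infer that all three rules yield negative durations. Only the day-missing rule can, because the other two suppress the calculation.
- A reader might infer that the error compounds, because SAP 8.2 treats a missing relationship as related. That needs a second missing field on the same event, and Protocol 10.3.3 obliges the investigator to assess causality for every event.
- A reader might take 4 of 17 weeks as the frequency of the problem. It is only the largest share of the study that precedes dosing. It says nothing about how often a resolved pre-dose event has a known end and an incomplete start.

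**Conclusion.** The point holds as a minor error in a stated rule. In three branches, SAP 8.2 counts as treatment-emergent an event whose recorded end date shows that it is not. In the day-missing branch it also produces a zero or negative duration; in the other two only the false flag stands.

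The size is at most 3.3 percentage points per misflagged participant at 30 participants. The documents give no rate of partial dates, so no expected count can be calculated. Cases are probably few, and the bias runs towards more TEAEs.

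The conclusion rests on two assumptions. Duration is taken as end minus start, with or without one added day. The worsening limb of the TEAE definition is taken to mean worsening after the first application, since a worsening confined to screening could not be treatment-emergent.

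**What to change.** Add to SAP 8.2, for all three branches: *If the end date, or its latest possible value when partial, is before the first dose, the AE is not treatment-emergent.*

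Add for the day-missing branch: *In that case the 1st-of-month start is kept, and the imputed start may not be later than the end date.*

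Stating the duration formula in the same place would remove the remaining ambiguity.

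Using the latest possible end date keeps uncertain events as TEAEs, so the SAP's conservative intent is preserved. The cost is two sentences and one programming condition, with no new data. If the SAP is no longer open to change, the condition can be applied and recorded in the clinical study report, as SAP Section 1 provides for deviations.
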